## SUBJECT MANAGEMENT

### 6.0 Inclusion and Exclusion Criteria\*

#### 6.1 Eligibility Criteria:

AYA patients	Inclusion: 14-21 years, current or past 30-day ENDS use, hospitalized, English speaking  Exclusion: severe illness, severe psychiatric illness or cognitive impairment
Parents/Guardians	Inclusion: AYA agrees to parent/guardian surveys

Hospital Staff	Inclusion: Staff of enrolled AYA agrees to participate
----------------	--

**6.2 Equitable Selection:** There are no exclusions based on sex or race/ethnicity. We will plan to enroll a balanced study sample by reviewing the EHR and approaching a study population that is representative of the hospitalized AYAs at our hospital. As a majority of patients are English speaking we will plan to enroll English speaking participants, we will provide a parent information sheet in Spanish for participants whose parents speak Spanish but the enrolled participant must be English speaking.

**6.3 Vulnerable Populations:** *Check any vulnerable populations that are being targeted for enrollment into the study: (Members of the following populations may not be included as participants in the research unless selected here.)*

- Children/Minors (under 7 years of age)
- Children/Minors (7-17 years of age)
- Neonates (infants less than 30 days old)
- Neonates of Uncertain Viability (infants less than 30 days old)
- Non-Viable Neonates (infants less than 30 days old)
- Wards of the State
- Fetuses
- Pregnant Women
- Adults with impaired decision-making capacity
- CM Employees
- CM Students/Residents/ Fellows
- Economically or Educationally Disadvantaged Persons
- Prisoners

Adolescents aged 14-17 years:

Adolescent assent procedures will follow practices accepted by the Society for Adolescent Health and Medicine and current regulatory guidelines and align with those previously used for CM studies involving adolescents

All adolescents will be encouraged to ask questions, provided necessary time to consider participation, and able to stop participation at any time, should they choose to do so.

All adolescents will be assured that their decision to participate or not will have no impact on their relationship with and care received at CM.

Wards of the State:

Another population that requires close attention are those who are wards of the state. This population is extremely important to capture, as they are known to have higher risk

**SHORT TITLE:**

for all of the factors being studied here and likely benefit from prevention at every medical encounter.

Hospital staff as participants: We will enroll CMH employees (hospital staff) in the study. We will minimize the potential for employees to feel coerced or unduly influenced to participate in the study by ensuring that employee will not be recruited or enrolled by their direct supervisor. Participation in the study is completely voluntary and does not impact the AYA patient's participation.

**7.0 Local Number of Subjects**

144 AYA and up to 144 parents of AYA, up to 10 hospital staff members will be recruited at CMH (the lead study site).

**8.0 Identification and Recruitment of Potential Participants\***

**8.1 Identification of Potential Participants:**

How will participants be identified? (Check all that apply)

- Chart reviews
- By their treating physician who will then provide the study team's contact information to the potential subject/family
- By their treating physician who will obtain patient/family permission to share contact information with the study team
- By a partnering community-based organization who will then provide the study team's contact information to the potential subject/family
- By a partnering community-based organization who will obtain patient/family permission to share contact information with the study team
- Self-refer in response to IRB approved advertisements or websites
- Through Cerner or other CM sources (e.g. databases, billing records, pathology reports, admission logs, etc.) May involve access of records by individuals not involved in the patient's care.
- List of candidates provided through the Data Report Request Form
- Registry of individuals interested in research opportunities
- Past subject list

**SHORT TITLE:**

Participants will roll-over from another research study: Study # \_\_\_\_\_

Other: Hospital staff of enrolled AYA will be identified at bedside.

**8.2 Pre-Screening prior to HIPAA Authorization**

Will any of the identification methods checked above involve access to Protected Health Information (PHI) prior to obtaining HIPAA Authorization?

Yes

No

- *If yes, a “Partial Waiver of HIPAA Authorization” is required. Be sure to make this selection in the “HIPAA & Confidentiality” section below and complete [Addendum E: Waiver/Alteration of HIPAA Authorization](#)*

**8.3 Recruitment of Potential Subjects:**

All data collection will occur at CMH, the lead study site. The research team will use the EHR to identify and recruit a heterogeneous sample of eligible AYAs for the pilot RCT. The health educator will monitor the EHR to identify, notify the medical team and then enroll and consent eligible AYA participants. Recruitment will occur at flexible times to minimize hospital care disruptions. Hospitalized AYAs with current (past 30-day) ENDS use (including those with co-use of cigarettes) will be randomized 2:1 to receive our novel intervention or control intervention that will consist of brief advice and printed quit line referral. Data from AYAs and parents/guardians will be collected using confidential electronic survey collection via REDCap. The health educator will recruit, screen, consent, and randomize eligible participants. AYAs who decline to participate will be asked to provide age, sex, race and ethnicity to facilitate identification of participation bias.

Randomization of consented participants will be stratified on sex and age using a 2:1 ratio within strata via computer generated assignment sequence placed in sequentially numbered sealed envelopes.

Parents of enrolled AYA will be identified at the bedside or given a phone call to ask about interest in the study. The health educator obtain verbal consent from parents in person or by phone.

Hospital staff of enrolled AYA will be identified at bedside. The health educator will obtain verbal consent from hospital staff in person.

## 9.0 Surveys and Psychometric Testing:

- Data Collection:

All participants will complete a post-intervention survey and a 3-month survey sent via email, text message via Twilio, and/or mailed paper survey so the research team is not directly involved in outcome data collection.

Parents/guardians of AYAs will be asked to complete a post-intervention survey. Hospital staff of AYAs will be asked to complete a post-intervention survey and interview (n=up to 10). A member of the study team, the health educator will complete brief survey items and field notes after each session.

Measures: *Participant demographics and clinical characteristics* (e.g., age of initiation, nicotine dependence) will be assessed at baseline. The outcome measures, method of assessment, relevant stakeholders and detailed description are depicted in Table 3 and sample survey items in Table 4. *Preliminary efficacy* will be assessed via self-reported 30-day point prevalence tobacco/ENDS abstinence using the timeline follow-back method at 3-month follow-up. To obtain a biochemically verified outcome and to encourage accurate self-reporting we will assess salivary cotinine from all participants (not currently on NRT) who report abstinence. We will assess this by either mailing a saliva specimen home collection kit to then be return mailed (pre addressed and paid) to our study team or we will also offer the option of completing a home saliva cotinine test which do not require return mailing. For this option home saliva cotinine tests will be mailed to the participant. The study team will then schedule a secure Microsoft Teams video call to witness saliva test completion and results or photos of the test results can be emailed at a convenient time to [contact]. If video call is performed the Microsoft Teams video call will not be recorded. If photos are emailed, the photos will be uploaded to REDCap and then deleted from the email. Secondary efficacy outcomes will include self-reported motivation and confidence to quit immediately post-intervention and at 3-month follow up. We will assess *acceptability* with the overall intervention and intervention components via survey immediately post intervention (AYAs and parents) and at 3 month follow-up (AYAs). Acceptability will also be evaluated via participant enrollment and session completion rates. *Feasibility* will be assessed via intervention duration in minutes from audio recordings and [name] and the health educator will complete a brief survey and record field notes to assess feasibility (e.g., impact on workflow, disruption, suitability). To assess *fidelity* we will review audio recordings and rate health educator intervention and control sessions based on a previously developed fidelity rating scales.

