## SHORT TITLE: Tobacco Inpatient Intervention

self-reported abstinence with biochemical verification) as the primary outcome. We will also assess self-reported motivation and confidence to quit and implementation outcomes (i.e. acceptability, feasibility, and fidelity) immediately post-intervention and at 3-month follow up.

We will screen the EMR to identify potential eligible participants and send a text page to the medical team to notify them that we will approach the potential participant. The text page will state "Your patient is potentially eligible to participate in [name] research study about vaping and tobacco use. Please call us if you have concerns about our team approaching the patient." The study team will then approach the eligible participant and give brief information about the study (e.g., "We are doing a research project to learn how we can help adolescents and young adults stop vaping and using tobacco products. Are you interested in hearing more about this?"). The study team will then review and consent the eligible participants. Randomization of consented participants will be stratified on sex and age using a 2:1 ratio within strata via computer generated assignment sequence placed in sequentially numbered sealed envelopes. Control participants will receive brief advice from the health educator regarding tobacco and ENDS use cessation and printed referral to a quit line. Intervention participants will receive our vaping and tobacco use cessation intervention based in clinical practice guidelines and administered by a health educator. Intervention participants will be eligible to receive a prescription for nicotine replacement therapy based on current clinical practice guidelines if they demonstrate risk for nicotine withdrawal. All participants will complete a post-intervention survey and a 3-month survey sent via email, text message via Twilio, and/or mailed paper survey so the research team is not directly involved in outcome data collection. Four phone calls will be conducted on the intervention group post hospitalization to provide smoking cessation counseling. These calls will take approximately 30 minutes. Parents/guardians of AYAs will be asked to complete a post-intervention survey which will be administered by the health educator and will take approximately 15 minutes.

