## SHORT TITLE:

to our study team or we will also offer the option of completing a home saliva cotinine test which do not require return mailing. For this option home saliva cotinine tests will be mailed to the participant. The study team will then schedule a secure Microsoft Teams video call to witness saliva test completion and results or photos of the test results can be emailed at a convenient time to [[contact]](mailto:[contact]), a secure email address created specifically for this research study. Although accurate verification will not be possible with participants who are occasional users or those on NRT, this will also allow us to evaluate the feasibility of collecting saliva by mail or completing secure video or photos witnessed home saliva cotinine tests in this population which will be informative for future studies with daily ENDS users. Secondary efficacy outcomes will include self-reported motivation and confidence to quit immediately post-intervention and at 3-month follow up. We will assess *acceptability* with the overall intervention and intervention components via survey immediately post intervention (AYAs and parents) and at 3 month follow-up (AYAs). Acceptability will also be evaluated via participant enrollment and session completion rates. *Feasibility* will be assessed via intervention duration in minutes from audio recordings and [name] and the health educator will complete a brief survey and record field notes to assess feasibility (e.g., impact on workflow, disruption, suitability). To assess *fidelity* we will review audio recordings and rate health educator intervention and control sessions based on a previously developed fidelity rating scales To assess *preliminary efficacy*, differences in self-reported and biochemically verified 30-day tobacco/ENDS use abstinence at 3-month follow up (primary outcome) will be analyzed using a generalized linear model assuming an underlying binomial distribution and logit link function to compare between study arms. Motivation and Confidence to quit will be analyzed using a repeated measures analysis of variance. Potential differential outcomes based on sex and demographic factors will be explored. Chi-square (categorical variables) and Wilcoxon Rank Sum (continuous variables) tests will be used to assess participation bias. For acceptability, we will calculate the proportion of AYA participants and parents/guardians in the intervention arm with mean ratings of satisfaction and acceptability of  4 on the 5-point Likert scale. In addition, frequencies and percentages will be used to describe the enrollment and session completion rate. For *feasibility* we will conduct thematic analysis of field notes and conduct simple descriptive analyses (means, frequencies, percentages) of the brief survey items completed by [name] and the health educator and session length data. *Fidelity* will be summarized utilizing similar descriptive analyses of the fidelity ratings (e.g., percentage of intervention steps completed; mean rating of key MI skill adherence).

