Title: Development and Implementation of a Tobacco and ENDS Treatment Intervention for Adolescents and Young Adults in the Pediatric Hospital

Clinical Trial: NCT05936099

Date: August 30 2024

STATISTICAL DESIGN AND POWER

Aim 2: Evaluate preliminary efficacy and implementation outcomes of our tobacco and ENDS use intervention

Design: We will conduct a prospective, pilot trial with 3-month follow up to assess preliminary efficacy and implementation outcomes (Table 3). Hospitalized AYAs (n=144) with current (past 30-day) ENDS use (including those with co-use of cigarettes) will be randomized 2:1 to receive our novel intervention or control intervention that will consist of brief advice and printed quit line referral (see Figure 2). We will evaluate preliminary efficacy (i.e., 30-day self-reported abstinence with biochemical verification) as the primary outcome. We will also assess self-reported motivation and confidence to quit immediately post-intervention and at 3-month follow up and implementation outcomes (i.e. acceptability, feasibility, and fidelity).

Data Sources: AYAs: surveys, electronic health record; Parents/Guardians: surveys; Hospital Provider (i.e., [name]: survey, audio-recording of sessions; Health educator: survey, field notes, audio-recording of sessions

Assessments:

AYA Participants: We will use confidential, web-based surveys administered via Research Electronic Data Capture (REDCap) to capture AYA data pre- and post-intervention, 3-month follow up (Research Strategy Table 3 and 4, Appendix). The health educator will recruit, screen, consent, and randomize eligible participants. AYAs who decline to participate will be asked to provide age, sex, race and ethnicity to facilitate identification of participation bias. Randomization of consented participants will be stratified on sex and age using a 2:1 ratio within strata via computer generated assignment sequence placed in sequentially numbered sealed envelopes. *Control participants* will receive brief advice from the health educator regarding tobacco and ENDS use cessation and printed referral to a quit line. *Intervention participants* will receive the intervention developed in Aim 1, administered by the same health educator and [name]. All participants will complete a pre- and post-intervention survey and a 3-month survey sent via email, text message, and/or mailed paper survey so the research team is not directly involved in outcome data collection.

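### No pre-intervention measurement of motivation or confidence to quit is specified, protocol and SAP disagree on whether a pre-intervention survey exists, and the repeated measures ANOVA does not name its treatment effect

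*Protocol*

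**What the plan says.** Protocol 9.0 schedules the surveys of adolescents and young adults (AYAs) as follows: "All participants will complete a post-intervention survey and a 3-month survey". Protocol 5.1 has the same sentence. The SAP (Assessments, AYA Participants) has a different one: "All participants will complete a pre- and post-intervention survey and a 3-month survey". It also says that web-based surveys are used "to capture AYA data pre- and post-intervention, 3-month follow up". The SAP is dated August 30 2024, the date of the last entry in the protocol's revision history, so this is not a conflict with superseded text.

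On the outcome itself, Protocol 9.0 states: "Secondary efficacy outcomes will include self-reported motivation and confidence to quit immediately post-intervention and at 3-month follow up". The same two time points appear in the protocol's synopsis (1.1), Study Design (4.0), section 5.1, section 27.1 and Table 3, and in the SAP under Design and Assessments. At baseline, both documents plan to collect demographics and clinical characteristics, with age of initiation and nicotine dependence as examples.

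The analysis is one sentence, the same in Protocol 27.1 and the SAP: "Motivation and Confidence to quit will be analyzed using a repeated measures analysis of variance". Neither document says which time points enter the model, whether a baseline term is included, or which effect is of interest.

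**The concern.** Table 3 lists motivation and confidence under preliminary efficacy, which it defines as a contrast between intervention and control. A reader would therefore expect a defined treatment effect and, for an attitude score that varies widely between people, a starting value to adjust for. Followed as written, the protocol specifies no such value. The SAP names a survey that could hold it but does not say that it does.

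Three things are at stake. First, the trial could not report how far scores moved from before the bedside session. Second, it could not adjust for starting level, which would probably be a useful covariate for this outcome. Third, a repeated measures ANOVA with two post-session visits offers an arm term, a time term and an arm-by-time term. If the interaction were read as the treatment effect, a benefit of equal size at both visits would be missed.

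**Working it through.** **1. Time points side by side**

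| Item | Protocol | SAP |
|---|---|---|
| AYA surveys | after the session, 3 months (5.1, 9.0) | before and after the session, 3 months |
| Motivation and confidence | after the session, 3 months | after the session, 3 months |
| Baseline content | demographics and clinical characteristics, by example | the same |
| Model | repeated measures ANOVA, terms not named | the same |

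No place in either document schedules motivation or confidence before the session. The content of the SAP's pre-intervention survey is not stated, and Table 4, which holds the sample items, is not in the text available for this review.

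**2. What the two-visit model can estimate**

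Let d1 be the arm difference right after the session and d2 the arm difference at 3 months.
- Arm main effect = (d1 + d2)/2
- Arm-by-time interaction = d2 − d1

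If d1 = d2 = d, the main effect is d and the interaction is 0. Change from before the session cannot be estimated from either term. Change from the first visit to the second can be estimated by arm. In the intervention arm that interval also contains the four counselling calls described in Protocol 5.1.

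**3. Size of the precision loss**

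The documents give no SD, correlation, target difference or power for this outcome, so there is no stated figure to reproduce. The inputs are:
- 96 treatment and 48 control (Protocol 27.2, SAP Sample Size)
- alpha 0.05 (SAP Analysis), taken as two-sided because sidedness is not stated
- assumed: no loss to follow-up, one time point, 80% power, and a correlation r between baseline and outcome of 0.3, 0.5 or 0.7

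Formulas, in SD units:
- SE without baseline = √(1/96 + 1/48) = √0.03125 = 0.177
- SE with baseline = 0.177 × √(1 − r²)
- Detectable difference = (1.960 + 0.842) × SE
- Equivalent sample size ratio = 1/(1 − r²)

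| | SE | Detectable difference | Equivalent sample size |
|---|---|---|---|
| No baseline | 0.177 | 0.495 | 1.00 |
| r = 0.3 | 0.169 | 0.472 | 1.10 |
| r = 0.5 | 0.153 | 0.429 | 1.33 |
| r = 0.7 | 0.126 | 0.354 | 1.96 |

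At an assumed true difference of 0.4 SD, power is 62% without a baseline score and 66%, 74% or 89% with one.

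**4. Does this carry over to two visits?**

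For the arm effect averaged over both visits, assume the same r between all three measurements. The detectable difference without baseline is 0.495 × √((1 + r)/2). With baseline it is 0.495 × √((1 + r)/2 − r²). This gives 0.399 versus 0.371 (r = 0.3), 0.429 versus 0.350 (r = 0.5) and 0.457 versus 0.297 (r = 0.7). The gain remains.

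**The case against.** The case for leaving the plan alone has real force.

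- **Silence is not absence.** A reader might infer that motivation and confidence have no pre-intervention value at all. The documents do not support that. The baseline list is illustrative, the SAP's pre-intervention survey may carry the items, and a sentence listing outcome visits need not list a baseline. What stands is that no such measurement is specified, and that the two documents disagree on the survey.
- **Randomisation already answers the stated question.** Table 3 asks for intervention versus control, not change from baseline. A comparison of arms after randomisation is unbiased, and the arm main effect would detect a benefit that is equal at both visits. This stands fully. It does not tell the analyst which term to report.
- **Change can be shown.** It would be wrong to say that the trial cannot show change, since change from the post-session visit to 3 months is estimable by arm. It would also be wrong to call that interval mere drift after treatment, because the intervention arm's calls fall within it. For the same reason it cannot stand in for change from before the session.
- **Chance imbalance is not an extra harm.** Arms that differ by chance at the start are already part of the 0.177 SD standard error. Counting them again would count one loss twice.
- **This is a secondary outcome in a pilot.** The SAP leaves definitive efficacy to a later trial, and no power target is set for these scores. This limits the weight of the point, but the inconsistency and the undefined effect remain.

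**Conclusion.** The point holds as a gap in specification and a loss of precision. It is not a source of bias. The plan schedules no pre-intervention measurement of motivation or confidence, the SAP's pre-intervention survey is missing from the protocol's schedule, and the ANOVA names no treatment effect. As written, the trial cannot estimate change from before the session or adjust for starting level.

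At a single visit, a baseline score would cut the standard error by about 5% (r = 0.3), 13% (r = 0.5) or 29% (r = 0.7). These are 1 − √(1 − r²), and they do not depend on the numbers per arm. The absolute figures assume 96 and 48 participants with complete follow-up. The correlation is the weakest input, since the documents give none, and the benefit is small if r is near 0.3. A reader should not conclude that the secondary efficacy comparison is invalid. The change is worth making because it is cheap.

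**What to change.** 1. **Reconcile the schedules.** Add the SAP's pre-intervention survey to Protocol 5.1 and 9.0.
2. **Specify its content.** State in both documents that it carries the same motivation and confidence items as the later surveys, completed after consent and before the randomisation envelope is opened, so that the score cannot be influenced by the assigned arm.
3. **Define the effect.** In Protocol 27.1 and in the SAP under Measures and Statistical Analysis, replace the single ANOVA sentence. Define the treatment effect as the arm difference right after the session and at 3 months, each adjusted for the pre-intervention score. Say how participants without that score stay in the analysis.

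The cost is a few items on a survey the SAP already plans, with no new visit. The protocol already links a participant's surveys over time (23.1, 28.0). The drawback is that anyone enrolled without the items will have a missing baseline score.

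If enrolment is too far advanced for this to help, state instead that the analysis is a between-arm comparison at each post-session visit plus change from the first visit to 3 months, and note that this interval includes the intervention arm's calls. The survey schedules still need to be made to agree.

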## 10.0 Additional Research Activities

## SHORT TITLE:

**10.1** Data collection from the medical record: The research team will use a REDCap instrument to collect some demographic information (eg, age, insurance type) from the medical record for each participant.

Additionally, upon completion of enrollment, we will collect additional medical record data based on Cerner orders and/or prescription information (to assess for prescription of NRT).

**10.2** Refusal Log: The study team will maintain a refusal log to assess potential differences between AYAs that participate and those that do not. AYAs who decline to participate will be asked if they will provide information anonymously. If they agree to do this, they will complete an anonymous survey to assess age, sex, gender, race/ethnicity, primary language, and reason for not participating. This survey will be administered via REDCap/tablet computer. If the adolescent declines to complete the refusal survey, the study team member will complete survey items on age and sex (available via EHR) and reason for study declination, if provided.

**10.3** Blood and Other Specimen Collection:

- To explore the impact of genetic variation on electronic cigarette use, nicotine dependence and cessation outcomes, DNA will be isolated from each participant and genotyping/sequencing will be completed by CMRI Genomics core or a similar service. This will allow for detection of known SNPs of interest and creation of an exploratory dataset for future inquiry as new questions arise. To evaluate this exploratory outcome we will collect a salivary or salvage leftover blood (collected during hospital stay) samples from all participants at baseline.
- A saliva sample kit will be mailed to the participant's home with a pre-paid label for their return of the sample or participants will have the option of completing a salivary cotinine test at home that will be witnessed by a study team member through secured Microsoft Teams video calling or photos will be securely emailed to a research specific email address. If using the return mailing option participants will collect saliva according to included instructions and send the sample back in the package we provide them.
- No extra samples will be collected during this time.

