To assess *preliminary efficacy*, differences in self-reported and biochemically verified 30-day tobacco/ENDS use abstinence at 3-month follow up (primary outcome) will be analyzed using a generalized linear model assuming an underlying binomial distribution and logit link function to compare between study arms. Motivation and Confidence to quit will be analyzed using a repeated measures analysis of variance. Potential differential outcomes based on sex and demographic factors will be explored. Chi-square (categorical variables) and Wilcoxon Rank Sum (continuous variables) tests will be used to assess participation bias. For acceptability, we will calculate the proportion of AYA participants and parents/guardians in the intervention arm with mean ratings of satisfaction and acceptability of ≥ 4 on the 5-point Likert scale. In addition, frequencies and percentages will be used to describe the enrollment and session completion rate. For *feasibility* we will conduct thematic analysis of field notes and conduct simple descriptive analyses (means, frequencies, percentages) of the brief survey items completed by [name] and the health educator and session length data. *Fidelity* will be summarized utilizing similar descriptive analyses of the fidelity ratings (e.g., percentage of intervention steps completed; mean rating of key MI skill adherence). Potential differential outcomes based on sex and demographic factors will be explored. Chi-square (categorical variables) and Wilcoxon Rank Sum (continuous variables) tests will be used to assess participation bias.

Sample Size Our proposed *sample size* [$n=144$ (96 treatment, 48 control)] is well within the recommendations for behavioral intervention development pilot trials based on what is feasible to recruit in our hospital and judged to be sufficient to evaluate efficacy (i.e., self-reported/biochemically verified abstinence) in a preliminary behavioral design trial.^{63,64} With respect to percentage reporting self-reported and/or biochemically confirmed abstinence at 3-mo follow up the margin of error (ME) around our observed outcomes depends on the observed proportion with the largest ME occurring when the proportion is 50%. Our sample size is sufficient to provide a ME of 10% (if the proportion is 50%) or less. A study fully powered to determine efficacy will be the focus of an R01 hybrid implementation trial informed by this study.

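### The plan's assurance that the research team stays out of outcome collection does not cover the witnessed home cotinine test: no masking of the witness is described, and the video route leaves no record to re-read

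*Protocol*

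**What the plan says.** Protocol 5.1 and 9.0 and the SAP (Assessments) describe post-intervention and 3-month surveys delivered by email, text or post, "so the research team is not directly involved in outcome data collection".

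The primary outcome joins self-report to a biochemical check. The SAP states that "differences in self-reported and biochemically verified 30-day tobacco/ENDS use abstinence at 3-month follow up (primary outcome) will be analyzed" with a binomial model. On who is tested, Protocol 9.0 says "we will assess salivary cotinine from all participants (not currently on NRT) who report abstinence".

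The protocol offers three verification routes:

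- **Mailed specimen:** "mailing a saliva specimen home collection kit to then be return mailed (pre addressed and paid) to our study team".
- **Home test by video:** "The study team will then schedule a secure Microsoft Teams video call to witness saliva test completion and results". Protocol 10.3 describes the test as "witnessed by a study team member through secured Microsoft Teams video calling". Protocol 9.0 adds: "If video call is performed the Microsoft Teams video call will not be recorded".
- **Home test by photo:** "If photos are emailed, the photos will be uploaded to REDCap and then deleted from the email".

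Revision 7 in the Revision History (2.21.24) added a further salivary testing option. The SAP, dated August 30 2024, still describes mailed samples only.

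Protocol 8.3 has the health educator recruit, consent and randomize. The SAP has the same health educator deliver both the control advice and the intervention. Protocol 4.0 and 5.1 together have the health educator make the post-discharge counseling calls, which go to the intervention group.

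**The concern.** The remote-survey sentence is the only protection the documents offer against staff influence on the outcome. It works for the self-reported half. It does not reach the biochemical half once a team member watches the home test, because that result decides whether a reported quitter counts as abstinent.

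Neither document says who the witness is, whether that person may know the arm, who makes the positive or negative call, what cotinine cut-off applies, or how an unclear result is classed. A team member could follow the protocol to the letter, know the arm, judge a test over video, and leave nothing that a second person could examine. Because only reported abstainers not on NRT are tested, a small number of readings carries the primary result.

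**Working it through.** **Plan's own figure.** The only design figure is a margin of error of 10% or less at a proportion of 50%, with 96 treatment and 48 control participants. Margin of error = 1.96 × √(0.25/n):

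- n = 144: 8.2%
- n = 96: 10.0%
- n = 48: 14.1%

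The stated figure is reproduced for the whole sample and the treatment arm, but not for the control arm. The present point does not rest on it.

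**Routes side by side.**

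| Route | Team member sees the result live? | Something to re-read? | In the SAP? |
|---|---|---|---|
| Mailed specimen | None described | Specimen is returned | Yes |
| Home test, photo | No | Yes, image in REDCap | No |
| Home test, video | Yes | No | No |

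Only the video route combines a live view by the team with no retained record.

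**Weight of one reading.** Control: 1/48 = 2.1 points. Intervention: 1/96 = 1.0 point.

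**How many readings there might be (assumed).** If 25% to 40% report abstinence and all are tested, that is 24 to 38 tests in the intervention arm (96 × 0.25; 96 × 0.40) and 12 to 19 in the control arm (48 × 0.25; 48 × 0.40). With one third by video, about 8 to 13 and 4 to 6 tests respectively would leave no image.

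**Size of a one-arm misreading (assumed).** Let *s* be the self-reported abstinence rate, *t* the true verified rate (equal in both arms), *v* the share of tests by video, and *m* the share of positive video tests called negative in the intervention arm only. None of these is in the documents. Then

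bias = (*s* − *t*) × *v* × *m*.

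The rejection rate is that of a two-sided 5% pooled two-proportion z test, 96 against 48, normal approximation, with no true difference. The SAP gives α = 0.05 without sidedness; two-sided is assumed.

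| *s* | *t* | *v* | *m* | Bias (points) | Rejection rate |
|---|---|---|---|---|---|
| 25% | 15% | 1/3 | 10% | 0.3 | 5.0% |
| 25% | 15% | 1/3 | 30% | 1.0 | 5.1% |
| 40% | 20% | 1/3 | 30% | 2.0 | 5.6% |
| 25% | 15% | 1 | 30% | 3.0 | 6.8% |
| 40% | 20% | 1 | 50% | 10.0 | 23.7% |

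Last row in full: bias = 0.20 × 1 × 0.50 = 0.10, so the observed rates are 30% and 20% and the pooled rate is (96 × 0.30 + 48 × 0.20)/144 = 0.267. The standard error is 0.0782 under the null and 0.0743 unpooled. The upper-tail probability is Φ((0.10 − 1.96 × 0.0782)/0.0743) = Φ(−0.72) ≈ 0.237; the lower tail is negligible.

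**The case against.** **The sentence concerns the surveys.** This stands as a reading of its place in the text: it explains why surveys go out remotely, and self-report does stay self-administered. The test can only confirm or overturn a report of abstinence in someone not on NRT. But the sentence speaks of outcome data in general, and no separate safeguard is given for the test.

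**A reader might infer that the witness is unmasked and records the result.** The documents do not say so. They name only a study team member who witnesses. What can be said is that no masking is described and nothing bars the health educator, who knows the arm, from the task.

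**A reader might infer that home-test results cannot be checked.** That is true of one route in three. Photos are kept, and the mailed route yields a specimen.

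**A reader might infer that a few readings would turn a null result into a significant one.** Such an example can be built: 19/96 against 5/48 gives an odds ratio of 2.12 (Wald p = 0.16), and 19/96 against 3/48 gives 3.70 (p = 0.044). It needs two of five control results changed, both in the same direction, both by video, and none in the other arm. With only one changed (19/96 against 4/48), p = 0.086. It shows that small counts are fragile, not what bias to expect.

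**This is a pilot.** The SAP leaves a fully powered efficacy test to a later trial, so crossing 0.05 matters less. Even so, abstinence is the declared primary outcome, is compared between arms, and is meant to inform that later trial.

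**Conclusion.** The point holds in limited form. The plan's statement that the team stays out of outcome collection does not fit the witnessed home test, which feeds the primary outcome. No masking of the witness is described, and the video route keeps no record.

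The size of any bias cannot be fixed from the documents, because the share of video tests is not given. Across the assumed range it runs from 0.3 to 10 points, with a false-positive rate of about 5% to 24%. In the milder case (one third by video, 30% of positives misread in one arm) it is 1 to 2 points and 5.1% to 5.6%, which is close to nominal. The documents give no evidence that biased reading has occurred or is intended.

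The change is worth making because it is cheap and because a video result seen without an image cannot be recovered later.

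**What to change.** 1. In Protocol 5.1 and 9.0 and the SAP, limit the sentence on the team's non-involvement to the surveys.
2. For every home test, including those done by video, save a photo of the test result only (no face) to REDCap under the study number. Emailed photos already go to REDCap.
3. Have an existing team member who delivered no sessions and is not shown the arm make the positive or negative reading from that image, and use that reading in the analysis. Anyone who reviewed session recordings for fidelity will have learned the arm and should not be the reader. State beforehand how an unclear result is classed; masking alone leaves that to discretion.
4. Report the verification route by arm, and add the home test to the SAP.

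Cost: a short amendment, a REDCap field and a few minutes per tested participant, with one existing team member kept unaware of arm. Consent wording may need to change, because an image would now be kept from video calls that the protocol says are not recorded; Revision 7 itself carried a consent change. Video tests already completed without an image cannot be re-read and should be reported as such.
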